3.4.8.2. PGI-S

The PGI-S consists of 5 questions that ask the study participants to evaluate the severity of their appetite loss, fatigue, physical function, limitations of physical activity and walking over the past 7 days, on a 5-point verbal response scale that ranges from "None" to "Very severe".

The PGI-S is recommended by FDA for use as an anchor measure to generate an appropriate threshold that represents meaningful within individual change in the target patient population.

The change from baseline in PGI-S will be calculated for all post-baseline timepoints.

3.4.9. Tumor status according to RECIST 1.1 guidelines using CT scan at Week 12

CT scans will be acquired during the study to monitor the tumor burden. Monitoring of the tumor burden will be performed by the site following standard RECIST 1.1 criteria (outlined in Appendix 11 of the protocol).

3.4.10. Change from baseline in LSMI derived from CT scans at Week 12; Percent change from baseline in skeletal muscle and adipose tissue measures derived from CT scans at Week 12

CT scans will also be submitted to a central imaging vendor for the measurement of body composition (skeletal muscle area and adipose tissue areas at the 3rd lumbar vertebral level).

The endpoints are:

- LSMI (cm²/m²): LSMI = skeletal muscle area (cm²) / height (m)²
- Skeletal muscle area (cm²)
- Subcutaneous adipose area (cm²)
- Visceral adipose area (cm²)
- Intramuscular adipose area (cm²)
- Skeletal muscle radio-attenuation (Hounsfield Units, HU)
- Subcutaneous adipose radio-attenuation (Hounsfield Units, HU)
- Visceral adipose radio-attenuation (Hounsfield Units, HU)

Intramuscular adipose radio-attenuation (Hounsfield Units, HU)

Baseline is defined as the last measurement prior to, or on, study day 8. Change from baseline for LSMI will be calculated for all post baseline timepoints.

Percent change from baseline for the remaining skeletal muscle and adipose tissue measures will be calculated for all post baseline timepoints.

Percent change from baseline in radio-attenuation measurements at post baseline timepoints will be excluded for a participant if the IV contrast used at that timepoint is different to that used at baseline.

Additional exploratory body composition measurements may be performed but may not be reported in the CSR.

3.4.11. Change from baseline albumin and pre-albumin levels at Week 12

Albumin and pre-albumin will be assessed as a biomarker for nutritional status. A serum sample of approximately 6 mL will be collected for measurement of albumin and pre-albumin as specified in the Protocol.

The fold change from baseline in albumin and pre-albumin will be calculated for all post-baseline timepoints.

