
A listing of unbound and total GDF-15 serum concentration levels, sorted by treatment group, participant and timepoint, will be produced. The listing will also include the fold change from baseline and will include all participants and all timepoints. For unbound GDF-15, the listing will also include a column to indicate whether the absolute GDF-15 concentration is below the healthy volunteer median level or not.

Additionally, the following presentations for unbound and total GDF-15 serum concentration levels will be produced, separately for 1) all participants (excluding Week 9 and 11 timepoints) and 2) for only participants in the PK substudy (including all timepoints):

- A summary of concentrations (absolute values and fold changes from baseline) by treatment group and timepoint, where the set of statistics will include (as data permit) n, arithmetic mean, SD, CV%, minimum, Q1, median, Q3, maximum, geometric mean, geometric CV% and the number of concentrations above the LLQ
- A summary of whether the absolute unbound GDF-15 concentrations are below the healthy volunteer median level or not, by treatment group and timepoint, as described in Section 5.2.2
- Median concentration-time plots (for absolute values only) (on a linear scale, all treatments on the same plot), Q1 and Q3 may be included
- Mean (±SD, if appropriate) concentration-time plots (for absolute values only) (on a linear scale, all treatments on the same plot).

In all presentations, the fold changes will be presented as percent change from baseline ([fold change from baseline -1]*100).

Note that the separate presentations for the participants in the PK substudy may be reported in a supplemental CSR rather than the main CSR.

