Absolute values and changes from baseline in PGI-S will be summarized descriptively by treatment group and timepoint as described in Section 5.2.2.

6.4.9. Tumor status according to RECIST 1.1 guidelines using CT scan at Week 12

The overall tumor response will be summarized by treatment, as described in Section 5.2.2, using the categories defined in Appendix 11 of the protocol.

6.4.10. Change from baseline in LSMI derived from CT scans at Week 12; Percent change from baseline in skeletal muscle and adipose tissue measures derived from CT scans at Week 12

Absolute values and changes from baseline in LSMI will be summarized descriptively by treatment group and timepoint, as described in Section 5.2.1.

Change from baseline in LSMI will be analyzed using ANCOVA as described in Section 5.2.5. Additional terms for type of therapy [i.e. platinum or not] and type of cancer will be fitted in the model.

Absolute values and percent changes from baseline in skeletal muscle and adipose tissue measures (listed in Section 3.4.10) will be summarized descriptively by treatment group and timepoint, as described in Section 5.2.1.

6.4.11. Change from baseline albumin and pre-albumin levels at Week 12

Absolute values and fold changes from baseline in albumin and pre-albumin will be summarized descriptively by treatment group and timepoint, as described in Section 5.2.1.

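### Percent change from baseline is planned for four CT attenuation measures in Hounsfield units, where a negative or near-zero baseline gives a reversed or unstable result (minor)

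*SAP*

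**What the plan says.** SAP 3.4.10 lists nine CT body-composition endpoints: LSMI, four areas in cm² (skeletal muscle; subcutaneous, visceral and intramuscular adipose) and the radio-attenuation of the same four tissues in HU.

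Change from baseline is assigned to LSMI. For everything else the rule is: "Percent change from baseline for the remaining skeletal muscle and adipose tissue measures will be calculated for all post baseline timepoints". That this is meant to include the HU measures is clear from the sentence that follows, which deals with scans taken under different contrast conditions: "Percent change from baseline in radio-attenuation measurements at post baseline timepoints will be excluded for a participant if the IV contrast" differs from the one used at baseline.

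SAP 6.4.10 carries the rule into reporting: "Absolute values and percent changes from baseline in skeletal muscle and adipose tissue measures (listed in Section 3.4.10) will be summarized descriptively by treatment group". The tables are also split by timepoint. Absolute change in HU is not planned. Neither section gives a formula for percent change in the CT measures, or a rule for a negative or near-zero baseline.

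In Protocol Section 3 the matching endpoint is exploratory. It speaks of percent change in muscle and adipose measures and does not name radio-attenuation. Protocol 8.3.7.2 describes the central reading in terms of areas, while allowing additional exploratory measurements.

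**The concern.** Percent change is meaningful when the scale has a true zero and the baseline is positive. The areas in cm² meet both conditions. HU does not: water is set at zero by convention, and fat lies below it.

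Two consequences follow.

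- **Sign.** For a negative baseline, dividing the change by the baseline reverses its sign. A rise in fat attenuation is reported as a percentage fall, and a fall as a percentage rise.
- **Stability.** For a baseline near zero the ratio can become very large. A group mean can then be set by one or two participants with low muscle attenuation.

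At stake is whether the attenuation tables can be read at face value. No confirmatory result is involved.

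**Working it through.** The documents give no HU value, sample size or target for these measures, so there is no planned figure to reproduce. The check is on the behaviour of the metric. All HU values below are assumptions, with fat between -120 and -30 HU and muscle between -5 and +50 HU.

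**Formula.** Percent change = 100 × (post − base) / base. The SAP gives no formula for the CT measures. The one it writes out, for GDF-15 in 6.4.4, is 100 × (post/base − 1), which is algebraically the same and uses the signed baseline.

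**Step 1: fat, true change +5 HU.**

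| Baseline | Follow-up | Percent change |
|---|---|---|
| -120 | -115 | 100 × 5/(-120) = -4.2% |
| -100 | -95 | 100 × 5/(-100) = -5.0% |
| -80 | -75 | 100 × 5/(-80) = -6.25% |
| -50 | -45 | 100 × 5/(-50) = -10.0% |
| -30 | -25 | 100 × 5/(-30) = -16.7% |

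A true change of -5 HU gives the same sizes with a plus sign. The reversal does not depend on which negative baseline is chosen.

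**Step 2: muscle.** A change of +3 HU is 100 × 3/30 = +10% from 30 HU and 100 × 3/5 = +60% from 5 HU. A change of +5 HU is +10% from 50 HU, +50% from 10, +250% from 2 and +500% from 1, and then -500% from -1.

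**Step 3: effect on a group summary.** Take five hypothetical muscle baselines of 35, 30, 25, 40 and 2 HU, each rising by 5 HU. The percent changes are 14.3, 16.7, 20.0, 12.5 and 250. Their mean is 62.7% and their median 16.7%, although every participant changed by the same amount.

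**Step 4: dependence on the zero point.** Adding 1000 to the scale leaves every change in HU as it was. The fat change from -100 to -95 is -5.0% on the HU scale and 100 × 5/900 = +0.56% on the shifted one. The muscle change from 40 to 45 is +12.5% and 100 × 5/1040 = +0.48%.

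**Step 5: alternatives.** Dividing by the absolute value of the baseline restores the sign (fat from -100 to -95 becomes +5.0%). It leaves the near-zero problem (muscle from 2 to 7 is still +250%) and the dependence on the zero point. Absolute change gives +5 HU in every one of these +5 HU cases.

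**The case against.** The strongest reply is that little depends on these tables. The measures are exploratory with no estimand. SAP 5.1 names LSMI as the only CT measure to be tested, and SAP 6.4.10 gives the ANCOVA to LSMI alone. The interim efficacy outputs in SAP 7.2.1 include LSMI but not the attenuation measures. All of this stands.

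Safeguards are also planned. SAP 6.4.10 tabulates absolute values at baseline and afterwards, and SAP 5.2.1 puts the median, with quartiles and/or range, beside the mean. A reader could therefore see the approximate direction, and a mean pulled by one low baseline would show against its median. This stands in large part. It is not a full remedy, because the absolute values are grouped by timepoint and the participants at baseline and Week 12 need not be the same (Protocol 9.5 assumes about 30% discontinuation). As written, the contrast exclusion also applies only to percent change. The percent-change table is thus the only planned within-participant, contrast-matched summary of attenuation.

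It is fair, too, that the documents give no HU values and no denominator. How often muscle baselines fall near zero is unknown, and an absolute-value denominator would remove the reversal.

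One argument does not stand. The SAP version history mentions an exclusion of radio-attenuation measurements in 3.4.10, which might suggest that the measures were dropped. The current 3.4.10 still lists all four and excludes only contrast-mismatched percent changes.

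**Conclusion.** The rule as written is unsuitable for the four HU measures. With the signed baseline as denominator, percent change in adipose attenuation has the reversed sign for any negative baseline (-4.2% to -16.7% for a true +5 HU over the assumed range). Percent change in muscle attenuation is unstable if baselines approach zero. The conclusion rests on the signed denominator and on fat lying below zero on the HU scale. The size rests on assumed values.

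A reader might infer that the study report would present fat attenuation as moving the wrong way, or that the comparison between arms would be biased. The documents do not support this. Absolute values are reported alongside. Where all baselines are negative the reversal applies to every arm alike, so it mislabels the direction and favours no arm. No test, model or planned decision uses these measures. Nor is it shown that muscle means would in fact be distorted, since the frequency of low baselines is unknown.

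Severity: minor. Percent change remains sound for the four area measures.

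**What to change.** Four aligned edits to the SAP:

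1. In 3.4.10, assign absolute change from baseline in HU to the four radio-attenuation measures, and keep percent change for the four area measures.
2. In 3.4.10, reword the IV-contrast exclusion so that it applies to change from baseline in radio-attenuation. If it stays tied to percent change, it would no longer literally cover these measures, and contrast-mismatched scans could enter the new summary.
3. In 6.4.10, align the reporting sentence: absolute values and changes in HU for attenuation, absolute values and percent changes for areas.
4. In 2.1, which now records no modifications, note the departure from the protocol's percent-change wording for muscle and adipose measures.

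The cost is a few sentences and a small programming change, with no new data. Protocol Section 9 lets the SAP modify the outlined analyses and requires an amendment only for major changes to the primary endpoint definition or analysis, so a protocol amendment does not appear necessary.

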3.4.12. Survival status at end of Part A

The survival status at the end of Part A will be recorded for each participant. End of Part A is considered Week 12 for all participants (regardless of whether they enter the optional Part B or not).

The time (days) to death during Part A (up to Week 12) will also be calculated for each participant.

3.4.13. Response as defined by a ≥3.5% increase from baseline in body weight at Week 12

Additionally, response, as defined by a ≥3.5% increase from baseline in body weight at Week 12, will be defined as having two levels: 'Response' and 'Non-response'. The former will be based on participants having a ≥3.5% increase from baseline in body weight at Week 12. Otherwise, participants will be classed as having a 'Non-response'. Participants with an intercurrent event of premature discontinuation of study intervention, prohibited procedure/medication or inadequate compliance prior to Week 12 will have their Week 12 value censored (if not missing). Missing or censored values at Week 12 will be imputed as described in Section 5.3.1. Participants who die during the study will be classed as having a 'Non-response' after imputation. This endpoint will be calculated similarly for Week 4 and Week 8.

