### Table 1. Schedule of Activities for Part A Double-Blind

Visit Identifier	Screening				I	Part A: Do	ouble-Bl	ind a		F/U Part A	ED Part A
Abbreviations used in this table may be found in											
Week #			4	5 b,c	8 d	9 c,e (PK	10 c,f	11 с,е (РК	12	16	
						substudy only)		substudy only)			
Day -relative to start of study intervention (Day 1)	-28 to -7	1	29	36	57	64	71	78	85	113	
Visit Window (Days)			±3	-3/+7	±3	±2	±7/±3 f	±2	±2	+7	
Blood sample for immunogenicity (ADA and Nab) i		Х	X		Х				Х	Х	Х
Blood sample for albumin & pre-albumin		Х							Х		Х
Study Intervention and Other Treatments											
Registration within IRT	X										
Randomization		Х									
Study intervention administration		Х	Х		Х				Xa		
Prior/concomitant treatment(s)	X	Х	Х		Х				Х	Х	Х
Assessments											
Efficacy											
Weight j	X	Х	X	Х	X		X		Х	Х	Х
PRO-CRCSD k	X	$\rightarrow$	$\rightarrow$	$\rightarrow$	$\rightarrow$	$\rightarrow$	$\rightarrow$	$\rightarrow$	Х		Х
PRO-PROMIS (fatigue 7A & physical function 8c) 		Х	X		Х				Х		Х
PRO-FAACT 		Х	X		Х				Х		Х
PRO-PGI-S (appetite, fatigue and physical function) 		Х	Х		Х				Х		Х
PRO-PGI-C (appetite, fatigue, and physical function) 			Х		Х				Х		Х
PRO-PGI-S (physical activity and walking) m	Х				Х		X		Х		Х
PRO-PGI-C (physical activity and walking) m					Х		X		Х		Х
Digital Measures-physical activity and gait n	X→				X→		$X \rightarrow$	$\rightarrow$	Х		Х
Comfort and Wearability Questionnaire for Digital									Х		Х
Measures (At clinic)											
Qualitative Exit Interview o									Х		Х
Safety											
CT scan p	X								Х		Х
Serious and nonserious AE monitoring	X	$\rightarrow$	$\rightarrow$	$\rightarrow$	$\rightarrow$	$\rightarrow$	$\rightarrow$	$\rightarrow$	$\rightarrow$	$\rightarrow$	$\rightarrow$
Retained Research Samples (not applicable for											
China)											
Retained research sample for genetics (Prep D1.5) q,r		X									

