• To evaluate the effect of ponsegromab compared to placebo on albumin and pre-albumin levels in participants with cancer, cachexia, and elevated concentrations of GDF-15.	• Change from baseline albumin and pre- albumin levels at Week 12.	• Not Applicable.
• To evaluate the effect of ponsegromab compared to placebo on survival in participants with cancer, cachexia, and elevated concentrations of GDF-15.	• Survival status at end of Part A.*	• Not Applicable.

\* Safety, tolerability and survival will also be characterized in Part B once all applicable participants have completed Part B of the study. These data will be reported as part of the supplemental CSR.

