Participants will undergo review of concomitant treatments, vital signs, and assessment for resolution of any treatment-related AEs through approximately 56 days following discontinuation of study intervention. Participants continuing to experience AEs at this point following discontinuation of treatment will continue to be followed at least every 4 weeks until resolution or determination, in the clinical judgment of the investigator, that no further improvement is expected. If the unresolved AE is considered by the investigator as possibly related to or associated with ADA formation, the participant will be asked to return for drug concentration and ADA blood sampling at up to 3-month intervals, until the last follow-up of the AE.

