#### 7.2. Participant Discontinuation/Withdrawal From the Study

A participant may withdraw from the study at any time at their own request. Reasons for discontinuation from the study include the following:

- Participant refused further follow-up;
- Lost to follow-up;
- Death;
- Study terminated by sponsor.

At the time of discontinuing from the study, if possible, an early discontinuation visit should be conducted. See the SoA for assessments to be collected at the time of study discontinuation and follow-up and for any further evaluations that need to be completed.

The early discontinuation visit applies only to participants who are enrolled/randomized and then are prematurely withdrawn from the study. Participants should be questioned regarding their reason for withdrawal.

If a participant withdraws from the study, they may request destruction of any remaining samples taken and not tested, and the investigator must document any such requests in the site study records and notify the sponsor accordingly.

If the participant withdraws from the study and also withdraws consent (see Section 7.2.1) for disclosure of future information, no further evaluations will be performed and no additional data will be collected. The sponsor may retain and continue to use any data collected before such withdrawal of consent.

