5. GENERAL METHODOLOGY AND CONVENTIONS

5.1. Hypotheses and Decision Rules

The null hypothesis of no difference between ponsegromab and placebo will be tested for each primary, and selected secondary (physical activity, FAACT and CRCSD) and tertiary (PROMIS-fatigue, PROMIS-physical function, LSMI and survival status) endpoints. The alternative hypothesis is that ponsegromab is superior to placebo. The Type I error rate (α-level) used for the statistical inference will be 5% (1-sided). Each dose of ponsegromab will be compared separately with placebo. No adjustment for multiple comparisons will be made.

For all other endpoints, the results of any statistical analyses are for exploratory purposes only and there is no formal hypothesis testing.

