6.4.12. Survival status at end of Part A

Survival status at the end of Part A (Week 12) will be summarized descriptively by treatment group and overall, as described in Section 5.2.2.

Time to death will be summarized descriptively by treatment group, as described in Section 5.2.1. A cumulative incidence plot, as described in Section 5.2.6 will also be produced. Time to death will be analyzed using a Cox-proportional hazards model, as described in Section 5.2.7. All deaths will additionally be listed.

6.4.13. Response as defined by a ≥3.5% increase from baseline in body weight at Week 12

Response as defined by a ≥3.5% increase from baseline in body weight will be summarized descriptively by treatment group and timepoint, as described in Section 5.2.2, with no imputation for missing data, including all post-baseline timepoints up to Week 12 (ie. Weeks 4, 8 and 12). Barcharts of the percentages over time will also be produced, with all treatments on the same plot.

The percentage of responses (and 90% CIs) at Week 12 will also be reported by treatment after multiple imputation for missing values as per Section 5.3.1. These responses will also be analyzed separately using a logistic regression model (as described in Section 5.2.8), where missing values will be imputed using multiple imputation as per Section 5.3.1. The logistic regression model will be fitted to the data at Week 12 only.

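### Survival at Week 12 is a tested exploratory endpoint for every participant, but nothing scheduled establishes vital status at Day 85 for those who leave early, and the plot's censoring rule discards some known deaths

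*SAP*

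**What the plan says.** Protocol Section 3 lists "Survival status at end of Part A" as a tertiary/exploratory endpoint for Part A. SAP 3.4.12 makes it universal ("The survival status at the end of Part A will be recorded for each participant") and sets the end of Part A at Week 12 whether or not the participant enters Part B. SAP 5.1 includes it among the tertiary endpoints to be tested ("PROMIS-fatigue, PROMIS-physical function, LSMI and survival status") at 5% one-sided. SAP 6.4.12 adds a summary by arm, a cumulative incidence plot and a model: "Time to death will be analyzed using a Cox-proportional hazards model".

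On collection, the relevant row of Protocol Table 1 is "Serious and nonserious AE monitoring". There is no survival or vital-status row. Protocol 7.1 keeps participants who stop study drug in the study and follows them with a review of concomitant treatments, vital signs and "assessment for resolution of any treatment-related AEs through approximately 56 days following discontinuation of study intervention". Vital status is not named. For participants who leave the study, Protocol 7.2 provides one visit, to be held if possible: "The early discontinuation visit applies only to participants who are enrolled/randomized and then are prematurely withdrawn from the study".

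On analysis, SAP 5.2.6 censors the cumulative incidence plot at discontinuation of the study or of study intervention. SAP Section 4 dates the latter at last dose plus 29 days. SAP 5.2.7 gives no censoring rule for the Cox model.

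**The concern.** An endpoint defined for everyone at a fixed day needs a way of learning everyone's status on that day. A participant who attends Week 12 is known to be alive, and a participant who dies under follow-up is known to be dead. The plan has no scheduled step for a participant who left before Day 85.

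The loss is unlikely to be random. Protocol 7.1 lists disease progression and hospitalisation among the reasons for stopping study drug, so those who drop out of view are plausibly sicker than those who stay. If their deaths are unrecorded, censoring in the time-to-death analysis is informative, and different exit rates between arms could hide or create a difference. SAP 2.2 classes this endpoint as safety.

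The censoring rule in SAP 5.2.6 is a second, independent problem. It acts even where the death is known.

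**Working it through.** **1. How a death gets recorded.** There are two routes.
- AE/SAE reporting (Protocol 8.4.1) runs from consent to at least the final planned follow-up visit, and ends sooner if consent for further data is withdrawn. Fatal progression is reportable within that period (Protocol 10.3.2).
- Death is a listed reason for leaving the study (Protocol 7.2).

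Once participation has ended, Protocol 8.4.1 does not oblige investigators to seek events. Of those they happen to learn about after completion, it requires reporting only where they judge the event reasonably related to study drug. An unrelated death from progression after exit therefore need not reach the database.

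**2. Follow-up against Day 85.** Doses fall on Days 1, 29 and 57 (Table 1). For a participant whose last dose was on day d:

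| Rule | d = 1 | d = 29 | d = 57 |
|---|---|---|---|
| Follow-up contact in SAP 3.2.4.1, d + 28 to d + 35 | 29–36 | 57–64 | 85–92 |
| 56 days counted from last dose, d + 56 | 57 | 85 | 113 |
| SAP Section 4 discontinuation date, d + 29 | 30 | 58 | 86 |
| 56 days counted from that date, d + 85 | 86 | 114 | 142 |

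The 56-day rule falls short of Day 85 only if its clock starts on or before Day 28 (28 + 56 = 84). Counted from the SAP's own discontinuation date, it always reaches Day 85. The firm gap is therefore departure from the study, which can happen at any time and has no later scheduled contact.

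**3. Deaths removed by the plot's rule.** Days between the censoring date and Day 85, for a participant who stops drug:
- one dose: 85 − 30 = 55 days
- two doses: 85 − 58 = 27 days
- three doses: the censoring date, Day 86, is past Day 85, so none

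A death in those 55 or 27 days is left out of the plot even if it was reported. That conflicts with SAP 3.4.12, which counts time to death up to Week 12 for each participant.

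**4. How many participants could be affected.** The plan gives no survival figure. The nearest are the design figures in Protocol 9.5: 168 randomised, about 120 completing, about 30% discontinuing. These agree approximately: 168 × 0.70 = 117.6, against 120. Early discontinuers number 168 − 120 = 48, or 168 × 0.30 = 50.4, which is 12 to 12.6 per arm of 42. At the planned rate this is an upper bound, because it includes deaths already recorded and participants who stop drug but stay under follow-up.

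**The case against.** The strongest reply is that most deaths will be captured. AE/SAE monitoring covers every Part A visit, follow-up and early discontinuation. Participants who only stop drug are meant to remain in the study (Protocol 7.1, 7.2.1). Protocol 7.2.1 points to public information when vital status is being measured, which an endpoint of this kind arguably satisfies. Protocol 7.3 provides for repeated contact attempts and, where permitted, locator agencies. The schedule describes itself as an overview and the CRF is not among the documents, so a vital-status field may exist. The endpoint is exploratory and unadjusted for multiplicity, and the Cox model may be dropped.

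Much of this stands. A reader might infer that deaths after stopping drug are simply not collected, or that the 56-day follow-up routinely ends too soon. The documents support neither: deaths are reportable while a participant is followed, and the 56-day shortfall depends on an early clock start that the SAP's date definition contradicts.

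Some of the gap remains. The route in 7.2.1 is conditional and subject to local law, the agencies in 7.3 are optional and concern lost participants, and neither is tied to Day 85. A participant who declines further visits but not record review has no scheduled check. A CRF field alone would not create a contact at Day 85. None of these points touches the censoring rule in SAP 5.2.6.

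**Conclusion.** The point holds as a gap in ascertainment and a conflict between SAP sections. Following the plan as written, deaths after early exit can be missed, and the cumulative incidence plot will omit some known deaths. That the loss falls on sicker participants is a reasonable inference from the listed reasons for stopping. The documents give no death rate by discontinuation status.

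The affected group is at most about 48 to 50 participants at the planned discontinuation rate. A reader might want to convert this into a count of missed deaths, but the documents do not allow it. If 25% to 100% of 50.4 discontinuers were out of view by Day 85 and 10% to 40% of those had died, both pure assumptions, the count would run from 50.4 × 0.25 × 0.10 = 1.3 to 50.4 × 1.00 × 0.40 = 20.2. That range is too wide to use as an estimate.

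Nor do the documents establish that the percentage alive will be overstated in any arm. That depends on how unknown status is tabulated, which the SAP does not say. Likewise, SAP 5.2.7 is silent on censoring in the Cox model, so bias there is a risk rather than a consequence of a written rule.

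The endpoint is exploratory, which limits the weight of the point, but the correction is cheap and worth making.

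**What to change.** **Protocol Table 1:** add a vital-status item at Day 85 for all randomised participants, including those who stopped drug or left early. Obtain it by phone, medical record or public source, within consent and local law. State that vital status is being measured, so that the condition in 7.2.1 is met.

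**SAP 3.4.12, 5.2.6 and 5.2.7:**
- Base survival status and time to death on this item for all evaluable participants. State this explicitly, because SAP Section 6 otherwise defaults to the Censored set.
- Count deaths to Day 85 regardless of drug discontinuation.
- Censor only at Day 85 or at the date last known alive, in both the plot and the Cox model.
- Report unknown status as its own category by arm.

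**Cost:** one CRF field, up to about 50 calls or record checks, and a protocol amendment with the ethics approval that entails. No extra visit is needed. Participants who have withdrawn consent to contact and record review may remain unknown, and the separate category makes their number visible.
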